2. STUDY OBJECTIVES AND ENDPOINTS

The primary, secondary and exploratory objectives and endpoints of this study are shown in [Table 1](#). The definition and detail of each endpoint will be described in section 5.

Table 1: Objectives and Endpoints

Objectives	Endpoints
Phase 1 Dose Escalation	
Primary	

 To investigate the safety and determine the recommended Phase 2 dose (RP2D) and dosing schedule of TAS3351 	
 Incidence of dose limiting toxicities (DLTs) Adverse Events Clinical laboratory tests Vital signs 12-lead ECGs Echocardiography/MUGA Ophthalmologic assessment Other safety assessments
Secondary	

 To evaluate the antitumor activity of TAS3351 	
 Objective response rate (ORR) per Response Evaluation Criteria in Solid Tumors (RECIST) v1.1 by investigator Duration of response (DoR) by investigator Disease control rate (DCR) by investigator Time on treatment Progression free survival (PFS; Patients in part A2 only) Overall survival (OS; Patients in part A2 only)

 To characterize the pharmacokinetics (PK) of TAS3351 and its active metabolite (TAS-05-14317) in plasma 	PK parameters including: 
 Maximum plasma concentration (C_{max}) Time to maximum plasma concentration (T_{max}) Area under the plasma concentration-time curve (AUC) Terminal elimination half-life ($T_{1/2}$)
Exploratory	

 To explore the relationship between exposures of TAS3351 and its active metabolite (TAS-05-14317) in plasma and QT prolongation 	
 Time matched plasma exposures of TAS3351 and its active metabolite (TAS-05-14317) and changes from baseline in QTcF

 To explore biomarkers for TAS3351 including their potential association with antitumor activity 	Described in separate biomarker analysis plan 
 Biomarkers

Objectives	Endpoints

 To explore metabolites of TAS3351 in plasma 	
 Metabolites of TAS3351 in plasma

Phase 1 Dose Expansion	
Primary	

 To explore the efficacy of TAS3351 	
 ORR per RECIST v1.1 by independent central review (ICR)
Secondary	

 To confirm the safety and tolerability of TAS3351 at the RP2D and dosing schedule 	
 Adverse Events Clinical laboratory tests Vital signs 12-lead ECGs Echocardiography/MUGA Ophthalmologic assessment

 To further explore the anti-tumor efficacy of TAS3351 	
 DoR by ICR/investigator PFS by ICR/investigator DCR by ICR/investigator ORR by investigator Intracranial ORR (icORR) by ICR/investigator Intracranial DoR (icDOR) by ICR/Investigator Overall survival (OS)
Exploratory	

 To explore biomarkers for TAS3351 including their potential association with efficacy 	Described in separate biomarker analysis plan 
 Biomarkers

 To explore the potential exposure-response associations for efficacy and safety 	Described in separate biomarker analysis plan 
 Exposures estimated by Population PK model and selected efficacy and safety measures

[figure not shown]
3. STUDY DESCRIPTION

3.1. Summary of Study Design

Study 10073010 is a first-in-human (FIH) Phase 1/2 study designed to determine the recommended Phase 2 dose (RP2D) and efficacy of TAS3351 in patients with locally advanced or metastatic non-small cell lung cancer (NSCLC) harboring an acquired C797S epidermal growth factor receptor (EGFR) mutation.

The study design is summarized in Figure 1.

Figure 1: Study Schema

3.2. Treatment Assignment and Blinding/Unblinding

This study will be a single-arm, open-label, phase 1/2 study.

Eligibility must be verified prior to patient enrollment. Upon eligibility verification, patient information will be entered into an Interactive Web Response System (IXRS). The patient should receive the first dose of study therapy within 3 days following entry into the IXRS.

The Phase 1 Dose Escalation is designed to evaluate 6 dose levels of TAS3351 from 50 to 700 mg/day using a Bayesian Optimal Interval (BOIN) design (see Protocol Section 6.1.1).

When a dose level has been determined to be safe in Part A1 and preliminary antitumor activity has been observed, up to 10 further patients may be enrolled at each of such dose levels (“back-fill” patients).

In case a second dose level of TAS3351 might be evaluated in Part B (see Protocol Section 4.2.2), an additional 20 patients with C797S EGFRmt will be enrolled in Part B. A total of 40 patients will be then randomized at a 1:1 ratio between the two treatment arms (i.e., TAS3351 dose levels).

3.3. Determination of Sample Size

Part A:

Part A1: Phase 1 Dose Escalation

There will be up to 40 evaluable patients enrolled using the BOIN (Bayesian optimal interval design) design, [REDACTED] A minimum of 3 patients at each dose level are required.

Part A2: Backfill patients

Approximately 20 patients will be added for “back-fill” cohorts as needed in the Phase 1 Dose Escalation. The additional information from these “back-fill” patients will broaden the amount of safety and preliminary anti-tumor activity data for TAS3351 at a potential active dose levels to inform the selection of the RP2D of TAS3351.

Part B: Phase 1 Dose Expansion

Approximately 40 patients (20 patients per cohort) will be enrolled in the Dose Expansion part of this study. Sample size considerations were based on estimating the proportion of responders with certain precision. If there will be 9 responders, a sample size of 20 patients per cohort would allow to exclude the current standard of care ORR of 25% (90% CI: 27.4%, 68.0%) at 2-sided significance level of 10%.

4. STUDY PERIODS, TREATMENT REGIMENS, AND POPULATIONS FOR ANALYSIS

4.1. Study Periods for Analyses

Study periods are defined in [Table 2](#).

Table 2: Definition of Study Periods for Analysis

Period	Definition
Study Period	From the day of the first ICF signature to the last day of Survival Follow-up Period
Screening Period	From the day of informed consent form (ICF) signature (up to 28 days before first dose) to the day before the first dose
Treatment Period	From the date of first dose of study drug (Day 1/PK lead-in for part A1) to the last day of dosing.
Safety Follow-up Period	30 (+3) days after the last day of dosing
Survival Follow-up Period	From the last day of Safety Follow-up period to death, or study completion, whichever happens first

4.2. Populations for Analysis

The analysis populations in the study are defined in [Table 3](#).

Table 3: Definitions of Analysis Populations

Analysis Population	Definition
All Consenting Population	All patients who signed an informed consent form (ICF).
All Treated Population	All patients who received at least one dose of the study drug. This is the primary population for dosing, efficacy and safety analyses.
DLT Evaluable Population	All patients in the Dose Escalation, except backfill patients, who either experienced a DLT during the 1st cycle of treatment including PK lead-in period, or who completed the 1st cycle without experiencing a DLT and with at least 80% of planned study treatments administered. This is the specific population for DLT summarization.
PK Analysis Population	All patients who received at least one dose of study drug and have at least one post-dose TAS3351 and/or TAS-05-14317 plasma concentration measurement will be evaluated for PK; unless significant protocol

	deviations may have affected the data or if key dosing information is missing. This is the primary population for PK analysis.
PK/ECG Analysis Population	All patients who received at least one dose of study drug, have a baseline and at least one post-dose ECG value, and have time-matched plasma concentrations to at least one post-dose ECG value.
Pharmacodynamic/Biomarker Analysis Population	All patients in the All-Treated Population who have at least one evaluable baseline and one evaluable post-dose pharmacodynamic/biomarker datapoint for analyses.

4.3. Timing of Analysis

4.3.1. Interim Analyses

No interim analysis is planned. Unplanned interim analyses may be performed if required for regulatory purposes or at the Sponsor's discretion.

4.3.2. Primary Analyses

The primary analyses for Phase 1 Dose Escalation (Part A) and Phase 1 Dose Expansion (Part B) will be performed once all patients in each part have completed the Safety Follow-up Period or at least 6 months have passed since the last patient in each part was enrolled, whichever occurs first.

5. STATISTICAL ANALYSIS

5.1. General Methods

Unless otherwise noted, the bulleted titles in the following subsections describe tabulations of discrete variables, by the frequency and proportion of patients falling into each category, grouped by dose level (with total). Summary table will be separated by part A1, part A2, part A and part B. Total of part A and part B will be added in disposition summary, study drug medication summary and overview of adverse events. All listings will be presented for part A and part B. Percentages given in these tables will be rounded and, therefore, may not always sum to 100%. Continuous variables will be summarized by treatment group (with total) using the mean, standard deviation, median, minimum, and maximum values.

Time to event distribution (i.e., PFS, OS and duration of response) will be estimated using Kaplan Meier techniques. Median survival time along with 95% CI will be constructed based on a log-log transformed CI for the survivor function $S(t)$. Rates at fixed time-points (e.g., PFS at 6 months) will be derived from the Kaplan Meier estimate and corresponding confidence interval will be derived based on Greenwood formula for variance derivation and on log-log transformation applied on the survivor function $S(t)$.

5.2. Study Conduct

5.2.1. Accrual

The accrual will be summarized per country and investigational site for informed consent patients. Informed consent date, first dosing date, protocol/amendment ICF version, version, country, investigational site will be presented in a by-patient listing of accruals.

5.2.2. Important Protocol Deviations

Important protocol deviation (ICH E3 Q&A (R1)) is defined as a subset of protocol deviations that may significantly impact the completeness, accuracy, and/or reliability of the study data or that may significantly affect the patient's rights, safety or well-being. These include important informed consent form (ICF) issues, eligibility criteria not met, discontinuation criteria not followed; wrong treatment, incorrect dose/overdose based on protocol definitions, important deviations based on protocol design, and other important Good Clinical Practice (GCP) deviations.

Important protocol deviations will be summarized and listed in the Clinical Study Report (CSR).

According to US Food and Drug Administration (FDA) guidance on conduct of clinical trials of medical products during COVID-19 public health emergency, updated in Aug 2021, protocol deviations related to COVID-19 and COVID-19 impact will be listed in the CSR.

5.2.3. Analysis Populations

The number of patients and percentages in each analysis population (based on all treated population) will be summarized for all treated population. Analysis population assignments for all treated population will also be listed.

5.2.4. Subgroup Analysis

If certain groups of patients (e.g., patients with brain metastases, regional specific analysis) become clinically interesting during the Escalation, subgroup analysis will be performed.

5.3. Study Population

5.3.1. Patient Disposition

Patients may be pre-screened for *EGFR* C797S status prior to the screening. These data will be captured in EDC screening folder. The number of patients who are pre-screened and their gender, *EGFR* status will be summarized and listed.

The total number of patients screened will be presented. Number of screen failures, number of patients not treated with study drug along with reason will be tabulated. Number of patients who discontinued treatment/study along with corresponding primary reason will be tabulated. Number of patients ongoing at time of data cutoff, and for part A1, number of patients who are DLT evaluable per dose level will also be tabulated.

Listings for informed consent patients will be provided showing each patient's informed consent date with protocol amendment version, date of re-consent, if available, reason for not being treated with study drug, first and last dosing date, date of study ending and primary reason for discontinuation of treatment and end of study. A listing to present DLT evaluable patient disposition for patients in DLT evaluable population of part A1 will be provided. A listing for patients not treated will also be provided, showing each patient's race, gender, age, and consent date.

5.3.2. Demographics

The following baseline characteristics will be summarized. Listings will also be provided.

- Age at the time of informed consent
- Age category (< 65, ≥65)
- Sex (Male, Female)
- Race (Caucasian/White, Black or African American, Asian, American Indian or Alaska Native, Native Hawaiian or Other Pacific Islander, Not collected, Other)
- Ethnicity (Hispanic/Latino, Not Hispanic/Latino, Unknown, Not collected)
- Country (USA, Japan, Germany, France, Netherlands (for A1); also, Italy, Spain, Korea for A2 and beyond)
- ECOG performance status (0, 1)
- Is/was the patient a tobacco smoker? (Yes/No)
- If the patient is/was a tobacco smoker, Brinkman index (piece/day*year)
- Baseline height

- Baseline weight
- Baseline BMI (= Weight (kg) / (Height (cm) / 100)²)

5.3.3. Baseline Disease Characteristics

The following nature and duration of cancer will be summarized. Listings will also be provided.

- Time since initial diagnosis (years)
= (Year of informed consent) – (Year of initial diagnosis) + 1
- Age at initial diagnosis
= (Age at the time of informed consent) – (Time since initial diagnosis)
- Time since confirmation of first metastasis (years)
= (Year of informed consent) – (Year of the first metastasis confirmed) + 1
- Cancer stage (TNM: I A1 to IV B) at the time of initial diagnosis
- Histology (Adenocarcinoma/Squamous cell carcinoma/Neuroendocrine tumors/Large cell carcinoma/Other)
- Grade of tumor (Well differentiated/Moderately differentiated/Poorly differentiated/Undifferentiated/Unknown)
- Presence and absence of CNS metastases
- New CNS metastases (yes/no)
- CNS metastases progressing after last treatment (yes/no)
- Patient with leptomeningeal disease (yes/no)
- Results of local tumor tissue/cfDNA analysis
 - Type of sample (Tumor tissue, cfDNA from blood sample)
 - Assay method (NGS, PCR, Other)
 - Type of EGFRmt (C797S/ Exon 19 Deletion/ Exon 20 insertion/ E709X/ G719X/ L858R/ L861Q/ L861R/ S768I/ T790M/ Amplification/ Other)

5.3.4. Medical History and Active Symptoms

Medical history (and Active Symptoms) will be coded according to the Medical Dictionary for Regulatory Activities (MedDRA), version 25.1 or later. Medical history and active symptoms will be summarized by System Organ Class (SOC) and preferred term (PT) respectively. These will be listed by patient.

5.3.5. Prior Anticancer Therapy

Prior surgery for lung cancer, prior radiotherapy for lung cancer, and prior systemic anticancer therapy will be summarized:

- The number and percentage of patients with at least one surgery for lung cancer will be presented. Outcome of surgery will be summarized. Surgery location, such as brain, will be listed as applicable.
- The number and percentage of patients with at least one prior radiotherapy for lung cancer will be presented. The intent of the radiotherapy (it is "treatment setting") and whether the radiation field includes the thoracic region (ie Yes/No) will be summarized.
- The number and percentage of patients with at least one prior systemic anticancer therapy for lung cancer will be presented. The preferred name of drug name per regimen coded with WHO Drug Dictionary will be summarized. The best response to therapy (CR, PR, SD, PD), the treatment modality (Chemotherapy, EGFR targeted, Immunotherapy, Antibody-drug Conjugate, Other EGFR targeted, other) the treatment setting (Neoadjuvant, Adjuvant, 1st line, 2nd line, 3rd line, 4th line, 5th line, 6th line, 7th line, 8th line, 9th line, 10th line, Other), the reason for the therapy discontinuation, duration of the anticancer therapy, and time from the end date of the anticancer therapy to the first dosing date of study drug will be summarized.

All collected information for prior surgery, prior-radiation therapy, and prior systemic anticancer therapy will be listed.

5.4. Concomitant Medication and Therapy

Medications and therapies taken on or after the first dose of study drug through 30 days after the last dose of study drug are considered concomitant medications and therapies. In addition, medications that started prior to the first dose of study drug and continued into the treatment period are considered concomitant medications and therapies. A medication is considered prior if the stop date of the medication is prior to the study drug start.

Concomitant medications/corticosteroids use for brain metastases will be coded with World Health Organization (WHO) Drug Dictionary (most up-to-date version at the time of analysis). Concomitant medications will be summarized by ATC level 2 (Therapeutic Main Group) and ATC level 4 (Chemical/Therapeutic Subgroup). Medications will be sorted in descending order of frequency of ATC level 2 and ATC level 4 within ATC level 2 in the total column. A patient will be counted only once within each level of summarization if the patient has taken a medication more than once. Medications will be reported using the generic name.

Concomitant therapies will be coded according to the WHO Drug Dictionary. It will be summarized by ATC level 2 (Therapeutic Main Group) and ATC level 4 (Chemical/Therapeutic Subgroup).

All concomitant medications and therapies will be listed. Detailed information about corticosteroid uses for brain metastases will be listed and summarized..

5.5. Efficacy Analyses

Unless otherwise specified, all efficacy analyses will be performed based on all treated population. The definition for confirmation and duration of overall response is presented in the protocol Appendix C.

The description of each efficacy endpoint is provided in [Table 4](#).

Table 4: Efficacy Endpoint Definitions

Endpoint	Definition
ORR	The proportion of patients experiencing a best overall response of PR or CR (per RECIST 1.1), based on IRC (and Investigator assessment). (investigator assessment only for part A)
DCR	The proportion of patients experiencing a best overall response of SD, PR, or CR (per RECIST 1.1), based on IRC (and Investigator assessment) (investigator assessment only for A)
DoR	For patients who demonstrated CR or PR as the best overall response, the time from the first documentation of response as CR or PR (per RECIST 1.1 based on IRC and Investigator assessment; investigator assessment only for part A to the first documentation of objective tumor progression or death due to any cause, whichever occurs first. If a patient does not progress or die following a response, then their DoR will use the PFS censoring time. - (Date of PD/death or censoring) – (date of first response of CR/PR(as BOR)) + 1.
PFS (All treated)	Time from date of first dose to the date of documentation of disease progression, or date of death, whichever occurs first - (Date of PD/death or censoring) – (date of first dose) + 1.
OS (All treated)	Measured from the date of first dose until the date of death due to any cause - (Date of death or censoring) – (date of first dose) + 1.

The best overall response (BOR) is determined once all the data for the patient, which are assessments obtained after study treatment discontinuation or starting a subsequent anti-cancer therapy, are known. The following best overall responses are defined based on the timepoint level response.

- Complete Response (CR): Required two timepoint assessments of CR, with the second at least 4 weeks after the initial CR. An intervening timepoint assessment of PR, SD, or PD will not be confirmed as CR.
- Partial Response (PR): Required a first assessment of PR and a second assessment of PR (or CR) at least 4 weeks after the initial PR. An intervening timepoint assessment of SD or PD will not be confirmed as PR.
- Stable Disease (SD): Assessed if the criteria for best overall response of CR, or PR are not met and if in addition, an assessment of SD (or better) has been documented at least once more than 6 weeks from the first dose of study drug.
- Progressive Disease (PD): Defined by any timepoint assessment of PD with no prior response qualifying as SD, PR, or CR.
- Not evaluable (NE): NE refers to patients with post-baseline tumor assessment(s) that are not evaluable.

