Adverse events	X	X	X						X	(X)	From signing ICF through 30-day safety follow-up or until start of new anticancer therapy, whichever is earlier. See Section 10.1 (X) only related SAE Investigator becomes aware of
Concomitant medications	X	X	X						X		From signing ICF through 30-day safety follow-up or until start of new anticancer therapy, whichever is earlier. See Section 6.4
ECOG Performance Status	X		X			X		X	X		

PK sampling		See Table 13 / Table 14									Table 13 for QD dosing / Table 14 for BID
Central ECG		See Table 13 / Table 14									To be performed as triplicates. For patients in Part A1 only. See Section 7.1.2
Local ECG ^c	X		X			X		X	X		12-lead ECG. Not needed if central ECG done the same day. Additional ECG monitoring as clinically indicated. See Section 7.1.2
Echocardiography/ MUGA	X							X			From Cycle 4 onwards, every 4 cycles or as clinically indicated. See Section 7.1.3
cfDNA blood samples			X			X		X	X		From Cycle 3 onwards, every other cycle. After 12 months, every 3 cycles.
Tumor tissue samples	X					(X)			(X)		Baseline sample optional for patients in Part A1. See Section 11.2 (X) On-treatment biopsy optional; can be done at one of these timepoints
Radiologic tumor assessment	X		X						(X)	(X)	Every 6 weeks (±7 days) from C1D1 irrespective of cycle. After 12 months, every 9 weeks (±7 days). (X) Patients who discontinue study treatment without radiographic PD will continue every 9 weeks (±7 days) until radiographic PD. See Section 7.1
Survival status										X	Every 3 months (±2 weeks); collect also further anticancer therapies. See Section 7.1 . For patients in Part A2 and B only
Administration of TAS3351		X	X								Continuous dosing See Section 6.1

^a PK lead-in period applies to Part A1 only: During PK lead-in period, patients will receive a single dose of TAS3351 3 days prior to the start of multiple TAS3351 dosing in Cycle 1 with subsequent PK blood collection. The PK blood sample collection times during the PK lead-in period may be found in [Table 13](#). For these patients, 72-hour post-dose assessments occur on C1D1, prior to C1D1 dosing.

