5.4. Discontinuation of Treatment

Discontinuation of study treatment does not represent a withdrawal from the study.

A patient must be discontinued from study treatment for any of the following reasons, but will continue to be monitored in the study:

1. Documentation of radiographic disease progression assessed by Investigator per RECIST v1.1* criteria.
2. Clinical progression.
3. Unacceptable AEs or change in an underlying condition such that the patient can no longer tolerate therapy, for instance any Grade ≥ 3 toxicity that does not resolve to Grade 1 or baseline (or to Grade 2 for toxicities that are manageable with supportive care) within 21 days should result in permanent discontinuation.
4. Physician's decision, including the need for other anticancer therapy not specified in the protocol or surgery or radiotherapy to the only site(s) of the disease being followed in the study.
5. Pregnancy or intent to become pregnant.
6. Termination of the study by the Sponsor.
7. At the patient's request at any time irrespective of the reason (including withdrawal of consent from further treatment with the study drug or follow-up).
8. Noncompliance with the study protocol that, in the opinion of the Investigator or the Sponsor, warrants withdrawal from treatment with the study drug.

Patients who withdraw consent for further study treatment may choose to remain on study and should continue with all study evaluations as outlined in this protocol. If the patient

withdraws consent to all follow-up assessments, the patient is considered to have discontinued the study.

* Note: If a patient demonstrates radiographic disease progression but continues to have clinical benefit (including stable performance status and absence of symptoms and signs indicating clinically significant progression of the disease), the continuation of TAS3351 may be considered in exceptional cases following consultation with the Sponsor and in accordance with the following criteria:

- Absence of unacceptable toxicity
- Absence of clinical symptoms or signs indicating clinically significant disease progression
- No decline in ECOG performance status
- Absence of rapid disease progression or threat to vital organs or critical anatomical sites (eg, CNS metastasis, respiratory failure due to tumor compression, spinal cord compression) requiring urgent alternative medical intervention.

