7.1.1. Efficacy Assessments

Efficacy assessments (including CT scan/MRI) will be performed by Investigator/local radiologist according to RECIST v1.1 guidelines at the timepoints outlined in the Schedule of Events (Section 1.3).

Radiological assessment must include MRI/CT of the chest, abdomen (and pelvis, if clinically indicated or obtained at baseline) at each time point, as well as assessment of all other known sites of disease. MRI of the brain should be performed if signs or symptoms suggestive of CNS metastases are present. The same method of assessment and the same technique must be used to characterize each identified and reported lesion at screening, throughout the study including the follow-up period. Contrast-enhanced CT scans or MRIs are the preferred methods for tumor assessments. If a contrast agent is contraindicated in a patient, obtain a non-contrast chest CT and enhanced MRI of the abdomen (and pelvis if clinically indicated). A CT should be performed using a ≤ 5 mm contiguous reconstruction algorithm.

For Part B and C of this study, all radiological imaging will be performed as indicated in the Site Imaging Manual provided by the central imaging core laboratory. Scans will be submitted to a Sponsor designated central imaging core laboratory for response assessment including RECIST v1.1, and/or exploratory analysis (eg, volumetric and viable tumor measurements). Detailed information regarding submission of images to the central imaging core laboratory is found in the Site Imaging Manual.

Note that complete response and partial response (PR) require confirmatory CT or MRI repeat assessment at least 4 weeks after the first detection of response. PET may be used to upgrade a response to a CR in a manner similar to a biopsy in cases where a residual radiographic abnormality is thought to represent fibrosis or scarring.²⁸

Patients who discontinue without documented radiographic disease progression per RECIST 1.1 should continue to undergo tumor assessments/scans according to the Schedule of Events until radiographic PD per RECIST v1.1 is documented, the study is completed, or consent is withdrawn.

7.1.2. 12-Lead Electrocardiogram

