9.2. Efficacy Endpoints

Efficacy endpoints based on radiographic imaging will be assessed per RECIST 1.1; endpoint definitions are summarized in [Table 15](#).

Table 15: Efficacy Endpoint Definitions

Endpoint	Definition
ORR	Proportion of patients experiencing a best overall response of PR or CR (per RECIST v1.1). Intracranial ORR be assessed based on ORR of CNS lesions only
DoR	Time from the first documentation of response to the first documentation of objective tumor progression or death due to any cause, whichever occurs first. Intracranial DoR be assessed based on DoR of CNS lesions only
DCR	Percentage of patients who have achieved a CR, PR, or stable disease (SD)
PFS	Time from date of first dose to the date of documentation of disease progression, or date of death, whichever occurs first
OS	Measured from the date of first dose until the date of death due to any cause

Abbreviations: CNS=central nerve system; CR=complete response; DCR=disease control rate; DoR=duration of response; ICR=independent central review; ORR=objective response rate; OS=overall survival; PFS=progression-free survival; PR=partial response; RECIST=Response Evaluation Criteria in Solid Tumors; SD=stable disease

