5.5.1. Objective Response rate (ORR)

Primary Analysis in Part B – ORR by ICR

The following analyses will be performed.

The best overall response will be tabulated, and ORR with 95% CI will be calculated using the Clopper-Pearson method. Confirmed and unconfirmed responses will be listed.

- For Part B, 2-sided 90% CI will also be provided.
- Waterfall plot of target lesion will be provided.

Secondary Analysis in Part A, B – ORR by investigator

The following analyses will be performed.

- The best overall response will be tabulated, and ORR with 95% CI will be calculated using the Clopper-Pearson method.
- Waterfall plot of target lesion will be provided.

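### As written, the SAP's best-overall-response sentence admits scans made on a later anticancer therapy, and no other text keeps them out of the Part B primary ORR

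*SAP*

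**What the plan says.** - **Data window.** SAP 5.5 determines BOR once "all the data for the patient, which are assessments obtained after study treatment discontinuation or starting a subsequent anti-cancer therapy, are known". ORR in SAP Table 4 is the share of patients whose BOR is PR or CR, so this sentence decides which scans count in "Primary Analysis in Part B – ORR by ICR" (SAP 5.5.1).
- **PR category.** Two PR scans (or PR then CR) at least 4 weeks apart are needed, and "An intervening timepoint assessment of SD or PD will not be confirmed as PR". This concerns only what falls between the two response scans.
- **PD category.** "Defined by any timepoint assessment of PD with no prior response qualifying as SD, PR, or CR".
- **Protocol definition.** Section 9.2 defines ORR as "Proportion of patients experiencing a best overall response of PR or CR (per RECIST v1.1") and gives no assessment window.
- **Scanning after treatment.** Protocol Table 1: "Patients who discontinue study treatment without radiographic PD will continue every 9 weeks (±7 days) until radiographic PD". Protocol 7.1.1 continues these scans "until radiographic PD per RECIST v1.1 is documented, the study is completed, or consent is withdrawn". Starting a new therapy is not among the reasons to stop.
- **Treatment beyond PD.** Under Protocol 5.4, "the continuation of TAS3351 may be considered in exceptional cases following consultation with the Sponsor".
- **Censoring.** SAP Tables 5 (DoR) and 6 (PFS) have no row for a new anticancer therapy. SAP 5.5 points to protocol Appendix C for confirmation and duration of response, but the protocol supplied contains only Appendix A.

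**The concern.** The purpose of ORR here is to measure response to TAS3351. A programmer who follows the SAP sentence would keep scans made after the patient has moved to another drug, and a response to that drug would be credited to TAS3351. Compared with a window that closes before new therapy, extra scans can add a best response but cannot remove one, so the error runs one way: ORR and DCR can only rise. DCR is more exposed than ORR, because a single scan of SD or better more than 6 weeks after first dose is enough for SD.

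The Part B results, together with the backfill patients, are meant to give proof of concept and lead to Part C (Protocol 4.2.2). With 20 patients per cohort, each response is worth 5 percentage points.

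**Working it through.** **1. The plan's own figure.** SAP 3.3 and Protocol 12.3 give a 90% CI of 27.4% to 68.0% for 9 responders in 20. The exact (Clopper-Pearson) limits are the 5% quantile of Beta(x, n−x+1) and the 95% quantile of Beta(x+1, n−x). For x = 9, n = 20 they are 25.9% and 65.3%. The printed interval is the exact 90% CI for 9/19. That is a separate error. 25% is excluded at 9/20 either way, and this point does not depend on it.

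**2. Does the text let the scans in?** Take a patient who stops TAS3351 without radiographic PD, for example for toxicity or because the physician decides other therapy is needed (Protocol 5.4), and then starts that therapy.
- Scans continue every 9 weeks; new therapy does not end them.
- Two successive scans are at least 7 weeks apart (9 weeks, with a ±7-day window on each), so the 4-week confirmation interval is met.
- No PD lies between the scans, so the PR rule is satisfied.
- The BOR sentence counts assessments made after a subsequent therapy starts.

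Result: confirmed PR in the primary ORR.

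**3. Is there a cut at first PD?** None is stated. The sequence SD (more than 6 weeks from first dose), PD, PR, PR meets the PR rule and not the PD rule. The sequence PD, PR, PR meets both, with no hierarchy given. But scheduled off-treatment scans end at radiographic PD, so scans after PD arise mainly when ICR and investigator PD dates differ, from unscheduled imaging, or in treatment beyond progression. This is the secondary gap.

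**4. Effect of one misattributed response in a cohort of 20.**

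| Responders | ORR | Exact 90% CI | Exact 95% CI |
|---|---|---|---|
| 8/20 | 40% | 21.7% to 60.6% | 19.1% to 63.9% |
| 9/20 | 45% | 25.9% to 65.3% | 23.1% to 68.5% |

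The 90% interval excludes 25% at 9 and not at 8. The 95% interval includes 25% at both.

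**5. How likely is one?** The documents do not say how many patients switch before radiographic PD. Assume 3 of 20, all non-responders to TAS3351. With response rate r to the next therapy, P(at least one) = 1 − (1 − r)³. Protocol 2.1.1 supplies two values of r:
- r = 4% (1 of 23 C797S patients on chemotherapy): 1 − 0.96³ = 0.115, about 12%.
- r = 25% (chemotherapy after osimertinib generally): 1 − 0.75³ = 0.578, about 58%.

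Both are before the second, confirming scan is required.

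**6. Effect on the chance of 9 or more in 20 when the true ORR is 25%.** Without contamination it is 4.1%. Let f be the share of TAS3351 non-responders scanned on another therapy (assumed). Apparent ORR = 0.25 + 0.75 × f × r; for f = 10%, r = 25% this is 0.25 + 0.75 × 0.10 × 0.25 = 26.9%.

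| r | f = 5% | f = 10% | f = 20% |
|---|---|---|---|
| 4% | 4.2% | 4.4% | 4.7% |
| 25% | 5.1% | 6.2% | 9.1% |
| 34.1% (top of the protocol's range) | 5.5% | 7.2% | 11.6% |

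**The case against.** **The sentence is probably a slip.** Read to the letter, BOR would rest only on scans made after treatment, which nobody intends. That stands, and it would be wrong to infer that the sponsor deliberately chose to count responses to other drugs. But the intended word could be 'excluding' or 'including', and the two give opposite rules for a primary endpoint.

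**The gap after PD is narrower than it looks.** A reader might infer that PD at week 6 followed by PR at weeks 12 and 18 on chemotherapy must be coded PR. The documents do not support this. That patient also meets the PD category, off-treatment scans are 9-weekly, and none is scheduled after radiographic PD. If the patient instead continues TAS3351 beyond progression, the later response is still on TAS3351. Dating DoR to the first PD scan would also give such a patient a negative duration, which suggests that responses after PD were not meant to count.

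**DoR.** A reader might also infer that the start of DoR is shifted in the drug's favour. A later start shortens the time to any given end date, so that direction is not established.

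**No test is at stake.** Protocol 12.2 states no formal hypothesis, and 12.7.3.1 summarises ORR descriptively with a 95% CI. Excluding 25% is a precision statement used for sample size, and no responder count is set for opening Part C. That stands. The estimate is still biased upward whether or not it is tested.

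**Few cases are likely.** The 4% rate is the protocol's figure for the C797S population that Part B enrols, confirmation needs a second scan, and the Part B cut-off may come 6 months after last enrolment or sooner. Response listings, swimmer plots and listings of later treatments would let a reader trace a misattributed response. All true, but a listing does not correct the ORR that is reported.

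**Conclusion.** The concern holds for scans made on a subsequent anticancer therapy. The SAP sentence admits them, no other text removes them, and the protocol's scan schedule can produce them. The missing cut at first PD is a lesser gap of the same kind.

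The firm part of the size is arithmetic: one misattributed response adds 5 points to a 20-patient cohort's ORR and separates 8/20 from 9/20 on the 90% interval. The frequency is not known. Roughly 12% to 58% for at least one such response rests on an assumed 3 of 20 switching and on chemotherapy rates of 4% to 25%, before confirmation; the lower end uses the rate for the enrolled population. The primary endpoint affected is that of Part B only: investigator-assessed ORR in Part A is secondary, and Part C lies outside this SAP. The sentence should be fixed before the analysis; it does not invalidate the design.

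**What to change.** Replace the sentence in SAP 5.5 with:

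> BOR is the best confirmed response among assessments from first dose up to and including the earliest of first PD by the same assessor (ICR for the primary analysis), the last evaluable assessment before any subsequent anticancer therapy, and data cut-off; later assessments are listed but not used.

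- Keep scans made after stopping TAS3351 but before PD or new therapy, so that late responses to TAS3351 are not lost.
- Apply the window to ORR, DCR, icORR and the set of responders for DoR and icDoR. Closing it at first PD also settles which category applies when PD comes before PR.
- Add a matching new-therapy row to SAP Tables 5 and 6. Otherwise a true responder who switches drug without PD goes on adding DoR and PFS time on the other drug.

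The cost is one sentence, two table rows and a date filter. Protocol Table 1 already collects further anticancer therapies at survival follow-up for Parts A2 and B. Part A1 has no survival follow-up, so the sponsor should check that the start date of later therapy is captured there. ORR may come out slightly lower.
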